1. INTRODUCTION AND RATIONALE

Parkinson's disease (PD) is a neurodegenerative disease affecting the motor, autonomic, cognitive, and sensory systems. It is a disease of the elderly: above the age of 55 years, the prevalence of PD is 1.4%.[1] In 2011, almost 60.000 patients in the Netherlands were estimated to have PD and due to ageing of the population an increase of at least 50% is expected in the following years.[2] PD is one of the diseases causing the largest reduction in quality of life and social functioning and the ability to work are impaired.

The core symptoms of PD are caused by the degeneration of dopamine producing neurons. At present there is no cure for PD, but several symptomatic therapies are available that mainly act upon the motor symptoms. Most of these (i.e., tremor, rigidity and bradykinesia) initially respond well to oral dopamine replacement although dyskinesias frequently occur after a variable period. Patients with advanced PD frequently show rapid and seemingly unpredictable swings between mobility, often with dyskinesias (ON-phase), and immobility (OFF-phase).[3] In the Netherlands, the prevailing treatment options for these patients are Deep Brain Stimulation (DBS) and Continuous intrajejunal Levodopa Infusion (CLI).[4] Continuous apomorphine infusion (CAI) is gaining more ground as another treatment option, since this treatment was researched in a recent double blind randomised controlled trial.[5]

For DBS, a neurosurgeon places two electrodes in the brain. These are connected to an implantable pulse generator. Patients continue with PD medications, though often at a lower dose.

For CLI, a gastroenterologist places a tube in the jejunum, which is connected to a portable pump. A levodopa-gel is continuously administered through the tube. In general, patients with CLI may stop other PD medications. Similar to DBS treatment, patients are hospitalized for placement of the tube and for the start of the levodopa-gel treatment. In both treatments, patients regularly visit the outpatient clinic to adjust the treatment.

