6.6 Dosages, dosage modifications and method of administration

For a description of posology and the method of administration see page 2 to 3, section 4.2, of the SPC (appendix 13.2).

Version 7: 23-10-2019 21 of 48

The total dose/day of Duodopa is composed of three individually adjusted doses: the morning bolus dose, the continuous maintenance dose and extra bolus doses.

Morning dose: The morning bolus dose is administered by the pump to rapidly achieve the therapeutic dose level (within 10-30 minutes). The dose is based on the patient's previous morning intake of levodopa and the volume to fill the tubing. The total morning dose is usually 5-10 ml, corresponding to 100-200 mg levodopa. The total morning dose should not exceed 15 ml (300 mg levodopa).

Continuous maintenance dose: The maintenance dose is adjustable in steps of 2 mg/hour (0.1 ml/hour). The dose is calculated according to the patient's previous daily intake of levodopa. When supplementary medicines are discontinued the Duodopa dose should be adjusted. The continuous maintenance dose is adjusted individually. It should be kept within a range of 1-10 ml/hour (20-200 mg levodopa/hour) and is usually 2-6 ml/hour (40-120 mg levodopa/hour). In exceptional cases a higher dose may be needed.

Extra bolus doses: To be given as required if the patient becomes hypokinetic during the day. The extra dose has to be adjusted individually, normally 0.5-2.0 ml. In rare cases a higher dose may be needed. If the need for extra bolus doses exceeds 5 per day the maintenance dose should be increased.

After the initial dose setting, fine adjustments of the morning bolus dose, the maintenance dose and extra bolus doses should be carried out over a few weeks.

Version 7: 23-10-2019 22 of 48

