- On-drug state time without troublesome dyskinesia -- mean hours per day in on-drug state without troublesome dyskinesia assessed with a 3-day motor symptom diary;
- Medication -- PD medication expressed in Levodopa Equivalent Daily Dose (LEDD, mg per day, including the continuous intrajejunal delivered levodopa)¹⁰;
- Functional health status -- Amsterdam Linear Disability Scale (ALDS) in on-drug state (29 items, score range 0-100) ¹¹;
- Cognitive performance -- Parkinson’s Disease Cognition Rating Scale (PD-CRS, score range 0-134) ¹²;
- Apathy -- Starkstein Apathy Scale (SAS, score range 0-42).¹³ Development of apathy was defined as newly scored apathy at 12-month follow-up (sum score ≥ 14 at follow-up and < 14 at baseline) and minimally 2 points increase in SAS score;

- Impulse-compulsive disorders and other compulsive behaviors -- Questionnaire for Impulsive-Compulsive Disorders in Parkinson's Disease (QUIP, utilizing established thresholds)¹⁴. Patients were considered to have developed an impulsive compulsive disorder, other compulsive behavior or compulsive use of medication if the QUIP criteria were met at 12-month follow-up and not at baseline. Impulsive compulsive disorder, other compulsive behavior or compulsive use of medication were considered to be resolved in case the QUIP criteria were not met at 12 months whilst they were fulfilled at baseline;
- Psychiatric diagnoses -- current and previous psychiatric diagnoses were assessed with the following subsets of the Mini International Neuropsychiatric Interview (MINI): major depressive episode, (hypo)manic episode, panic disorder, agoraphobia, social anxiety disorder, obsessive-compulsive disorder, alcohol use disorder, substance use disorder, and psychotic disorder.¹⁵ A new psychiatric diagnosis was defined as a current psychiatric diagnosis at 12-month follow-up, not being present at baseline. A psychiatric diagnosis was considered to be resolved in case it was present at baseline and not at 12-month follow-up;
- Harms -- (serious) adverse events ((S)AEs);
- Treatment course -- stopping the allocated treatment and switch to the alternative after initially receiving the allocated treatment (*i.e.*, switch from DBS to CLI or vice versa);
- Treatment satisfaction – number of patients that would recommend their treatment to others.

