If opportune, unit costs of (non-)hospital resources, working hours lost, and time spent on the patient by the primary care-giver were obtained from the most recent Dutch Manual on Costing in health care research (DMC).²³ The unit costs of the (re)placement of the neurostimulator system and of the tube and pump system (re)placements were based on unit costing sheets for distinct hospital care resources from the treatment center with the highest number of inclusions and subsequently capitalized based on a 5-year depreciation period (reflecting the lengths of their life cycles) in order to allow for a robust estimate of the difference in yearly treatment costs by study arm, irrespective of the chosen study's time horizon. The same hospital unit costing sheets, existing rates for mutual services excluding VAT, or passer-by prices (e.g., AMC Passantenprijslijst OZP, 2020) were used for observed diagnostic examinations and therapeutic procedures not listed in the DMC. Unit costs for medication were gathered from the Dutch Pharmaceutical Compass assuming standard prescriptions.^{26,27} The unit cost of lost working hours at the mean age of the included working patient at baseline was used, non-specific for gender. In case of prolonged continuous sick leave longer than the friction period, the friction cost method was applied.²⁸ The length of the friction period in days was calculated as the average over the study's observation period 2015-2020, weighted for the

yearly number of included patients, and equaled 97 days.^{23,29} Table EE1-S in the Supplementary Material shows unit cost of the resources used. Unit costs held for the base year 2020; unit costs originating from different calendar years were price-indexed with general yearly consumer price indices from Statistics Netherlands.³⁰

Costs of resources used were calculated by multiplying the frequency of distinct resources used with their respective (depreciated) unit costs. Volumes and costs (of health care used, out-of-pocket expenses, and productivity loss) are reported separately as (subtotal and total) means per patient per study arm.

Analyses were adjusted if deemed necessary in case of Parkinson-related or Parkinson non-related outliers in costs or QALYs. If related to Parkinson's disease, these were included and reported, if caused by unrelated comorbidities, these could have been excluded.

Health outcomes

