Appendix IV — Supplementary health economics tables

Table EE1-S. Dutch unit costs (€) for resources used

Resource	Unit	Unit costs in 2020 euros	Source
Screening for suitability			
preop. outpatient consultation	visit		DMC
inpatient stay	day		DMC
on/off-phase evaluation	procedure		hospital ledger
evaluation / nasogastric tube	procedure		passer-by rate
vitamin examinations	procedure		passer-by rate
other laboratory	procedure		passer-by rate
preop. anesthetic evaluation	procedure		hospital ledger
EKG	procedure		passer-by rate
MRI-brain	procedure		DMC
Infusion			
CLI-pump	device*		hospital ledger
CLI-cassettes	cassette		hospital ledger
PEG-jejunostomy placement	procedure*		passer-by rate
tube replacement	procedure*		passer-by rate
Stimulation			
(re)implantation	procedure*		passer-by rate
electrode replacement	procedure		hospital ledger
extension cable replacement	procedure		passer-by rate
battery exchanges	exchange		hospital ledger
Other hospital care			
Emergency department visit	visit		DMC
Hospital stay (in days)			
neurology ward	day		DMC
psychiatric ward	day		DMC
intensive care unit	day		DMC
other	day		DMC
Outpatient consultation			
neurologist	visit		DMC
CLI/DBS-nurse	visit		hospital ledger
neurosurgeon	visit		DMC
gastroenterologist	visit		DMC
PEG-nurse	visit		hospital ledger
psychiatrist	visit		DMC
(neuro)psychologist	visit		DMC
Imaging diagnostics			
MRI brain	procedure		DMC
CT brain	procedure		DMC
X-ray DBS leads	procedure		hospital ledger
CT abdomen	procedure		passer-by rate
ultrasonography abdomen	procedure		passer-by rate
Therapeutics			
explantation (battery, lead, ...)	procedure		passer-by rate
related medication	medication day		Pharmaceutical compass

Table EE1-S continued. Dutch unit costs (€) for resources used

Resource	Unit	Unit costs in 2020 euros	Source
Non-hospital care			
Medication			
CLI-cassettes related medication	cassettes medication days		Pharmaceutical compass Pharmaceutical compass
Out-of-hospital consultation			
general practitioner	visit		DMC
occupational therapist	visit		DMC
physiotherapist	visit		DMC
speech therapist	visit		DMC
dietician	visit		market price
social worker	visit		DMC
psychologist	visit		DMC
rehabilitation physician	visit		DMC
company physician	visit		DMC
Other institutional stay			
nursing home day	day		DMC
rehabilitation center day	day		DMC
Formal home care			
house holding	hour		DMC
personal	hour		DMC
home nursing	hour		DMC
Equipment			
walking devices	device		market price

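### Pricing medication per day at a standard prescription misses a lower dose of a continued Parkinson drug, which is the change the protocol expects with DBS

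*SAP*

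**What the plan says.** HEAP, Unit costs and costing, gives the price rule: "Unit costs for medication were gathered from the Dutch Pharmaceutical Compass assuming standard prescriptions". The term standard prescription is not defined. The same section gives the cost formula: "Costs of resources used were calculated by multiplying the frequency of distinct resources used with their respective (depreciated) unit costs".

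Table EE1-S (SAP document, Appendix IV) gives the counting units. Related medication under hospital therapeutics is counted per "medication day". In the non-hospital block the extracted text runs two units together ("cassettes medication days"): the cassette for the CLI gel and medication days for related medication.

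Protocol section 1 describes what is expected of other Parkinson drugs in each arm. For DBS: "Patients continue with PD medications, though often at a lower dose". For CLI: "In general, patients with CLI may stop other PD medications".

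The SAP's secondary outcomes include "PD medication expressed in Levodopa Equivalent Daily Dose (LEDD, mg per day, including the continuous intrajejunal delivered levodopa"). The between-group difference in mean change in this measure is to be reported. The HEAP does not mention it as an input to costing. None of the HEAP's missing-data scenarios, additional sensitivity analyses or scenario analyses varies the dose or price of medication.

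**The concern.** A cost built from days on a drug and a fixed price per day responds to stopping the drug, or to taking it on fewer days. It does not respond to a lower daily dose. The protocol expects mainly the first kind of change with CLI and the second with DBS. The rule can therefore register the drug saving typical of one arm and miss the saving typical of the other.

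The cost difference, CLI minus DBS, is the numerator of both the incremental cost-effectiveness ratio and the incremental cost-utility ratio (HEAP, Types of economic evaluation). An error of this kind is systematic. Bootstrapping the patients describes sampling variation around the charged costs and leaves the error in place. The trial could then report a fall in levodopa equivalent dose among its clinical results while its economic results show unchanged drug use for the same patients.

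**Working it through.** The documents give no oral drug price, no price per medication day and no expected dose reduction, so there is no stated medication cost to reproduce. The only planning figure usable for scale is the cost difference in Protocol section 4.4: 34,174 / 120,000 = 0.2848 QALY, which agrees with the stated 0.2847 apart from rounding. The sample size does not depend on the point made here.

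**1. What the rule registers.** Assume three drugs at €2 per medication day each, with true cost proportional to dose.

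- All three at the standard dose for a year: 3 × 2 × 365 = €2,190.
- All three continued at half dose: charged 3 × 2 × 365 = €2,190; costed by dose, 0.5 × 2,190 = €1,095. The saving of €1,095 is missed.
- One of the three stopped: charged 2 × 2 × 365 = €1,460. The saving of 2,190 − 1,460 = €730 is captured.

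**2. What this does to the difference between arms.** Let E be the mean charged drug cost minus the mean dose-based drug cost in an arm. The charged CLI-minus-DBS difference is then wrong by E(CLI) − E(DBS).

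- If CLI patients mostly stop other drugs, E(CLI) is near zero. If DBS patients continue below the standard dose, E(DBS) is positive. The difference is then understated.
- If the standard dose is below what these patients take, the sign reverses. A drug taken at 1.5 times the standard dose is charged 2 × 365 = €730 against 1.5 × 730 = €1,095 by dose, an undercharge of €365.
- If patients in both arms continue at lower doses, the two errors partly cancel.

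**3. Illustrative size.** Assumptions, none of them from the documents: €1,000–4,000 a year of oral Parkinson drugs at the standard dose, a 30–60% dose reduction after DBS on drugs that are continued, cost proportional to dose, and E(CLI) = 0.

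- Missed saving: 1,000 × 0.30 = €300 to 4,000 × 0.60 = €2,400 per patient-year.
- Share of the planned difference: 300 / 34,174 = 0.9%; 2,400 / 34,174 = 7.0%.
- Break-even QALY gain at €120,000: (34,174 + 300) / 120,000 = 0.2873; (34,174 + 2,400) / 120,000 = 0.3048. The shift from 0.2848 is 0.0025 to 0.02 QALY.
- Against sampling error, with the planned cost SD of €10,000 and 26 per group: SE = 10,000 × √(2/26) = €2,774. The missed saving is 300 / 2,774 = 0.1 to 2,400 / 2,774 = 0.9 of one SE.

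A wider set of assumptions (€1,000–6,000 a year, 20–60% reduction) gives €200–3,600, or 0.6–10.5% of €34,174.

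**The case against.** The strongest reply is that an undefined term is being read as a settled rule. The sentence describes where prices come from. A standard prescription could mean a standard daily dose, a pack or a dispensing quantity, and day prices could differ by strength. Nowhere do the documents say outright that dose is ignored. This stands as a limit on certainty. It does not remove the point: no step in the stated chain of price, unit and formula carries a dose, and a primary outcome's cost rule should not have to be guessed.

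Three stronger readings are tempting and are not supported.

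- A reader might infer that dose reduction after DBS has no effect at all on cost. A reduction achieved by dropping a drug does lower the count of medication days. Only a lower dose of a continued drug is lost.
- A reader might infer that the CLI gel is also mispriced, as if one cassette a day were charged whatever the volume used. Table EE1-S gives the cassette its own unit, Tables EE2a and EE2b report mean cassette use per patient, and the HEAP counts resource use by type. Nothing in the documents assumes one a day.
- A reader might infer that the bias certainly favours CLI. That needs the standard dose to exceed the dose DBS patients take, which the documents do not show. Oral co-medication is also allowed in the trial (Protocol section 5.2), so CLI patients who continue at a lower dose lose credit too.

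It is also fair to say that the size is modest and wholly assumed, and that recorded doses may be incomplete. Protocol section 7.3 and the schedule in section 12.4 provide for medication to be recorded at every visit without specifying dose. The levodopa equivalent dose outcome strictly needs doses only at baseline and 12 months.

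**Conclusion.** The point holds in a limited form. On the plain reading of the HEAP, non-cassette medication is charged per day at a standard prescription, so a lower daily dose of a continued drug does not change cost, while stopping the drug does. Because the protocol expects the arms to differ in just this respect, the rule can distort the cost numerator of both primary economic ratios.

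The likely direction, conditional on the standard dose being above the dose taken, is to overstate DBS drug cost and understate the CLI-minus-DBS difference. Neither direction nor size can be settled from the documents. The illustrative €300–2,400 per patient-year rests on assumed prices, assumed reductions, proportional cost and no offsetting error in the CLI arm. On those terms it is small to modest beside €34,174 and below one standard error of the planned difference. This is a worthwhile, inexpensive improvement to the costing method and gives no reason to expect the trial's conclusion to be overturned.

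**What to change.** In HEAP, Unit costs and costing, replace the standard-prescription assumption for Parkinson drugs with costing at the recorded dose: price per mg (or per tablet strength) × recorded daily dose × days. Use the drug-level medication records from which the levodopa equivalent dose is calculated. The pooled equivalent dose cannot itself be priced, because it combines different drugs.

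Keep a standard prescription only where no dose was recorded, for example for non-Parkinson drugs or visits without a dose, and define the term. State how a dose is carried from one visit to the next. Report standard-prescription costing for all drugs as a sensitivity analysis, so that the effect of the choice is visible. Cassette costing needs no change.

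The cost is HEAP wording, a more detailed medication price file and some programming. No new data collection is needed where doses were recorded. The carry-forward rule adds an assumption of its own if interim doses prove sparse.

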After baseline screening, patients eligibility for both treatments will be discussed with the appropriate disciplines (neurology, neuropsychology, neurosurgery, and gastroenterology) in the treating centre, or the centre that will provide the treatment. If any possible contraindications for one of the treatments is found, the patient will be excluded from the study. Possible contra-indications are a non-dopamine responsive tremor as main complaint or if the effect of dopaminergic medication on motor symptoms is too small. Subsequently, the patient is randomized using a web-based application. Dependent on the result of randomization, the patient will be treated in the own hospital or he or she will be referred to one of the cooperating DBS centres. Within 3 months after the baseline assessment the study-treatment — DBS or CLI — will be started. The treatment will be performed as described in section 5.1

At visits 2, 3, 4, 5, 6, 7 and 8 patients will undergo documentation of PD-medication, adverse events (through a standardized questionnaire), treatment failure and cross-over. The iMCQ, iPCQ, use of (informal) care and caregiver burden are assessed at visit 3, 4, 5, 6, 7 and 8. At visits 5, 6, 7 and 8 we will record the PDQ-39. At visit 6, 7 and 8 the patients

Version 7: 23-10-2019 25 of 48

will keep a motor symptom diary (3 days; including ON/ OFF phases, dyskinesias, and sleep states) and the Non Motor Symptom Checklist, ALDS and patient satisfaction with the treatment. At visit 6 we will record the MDS-UPDRS, the CDRS and blood analysis as described above will be repeated. Also, patients will undergo a short neuropsychological examination and standardized psychiatric assessment at visit 6 and 8. The first year of follow-up, a margin of one month is deemed acceptable in planning a visit, for the second and third year of follow-up, the visits will be completed within two months of the defined follow-up date.

Patient preference trial

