Originally, an intention-to-treat analysis (ITT) was planned as the primary analysis. Nevertheless, during the study it was observed that after allocation, several patients immediately refused CLI treatment and either chose to be treated with DBS or quitted study participation. Analyzing these patients in an ITT could have introduced a significant bias, as their apparent preference for DBS made them not representative of a population that considered CLI a suitable treatment for advanced PD. Furthermore, for the patients for whom post-baseline data were not available, all these data would have had to be imputed, contributing to the risk of bias. A modified intention-to-treat (mITT) population was introduced as the primary analysis, because analysis in the ITT population including all randomized individuals was considered less valid.⁷ The mITT population included all randomized patients who received the allocated treatment and continued in the RCT after randomization. Additionally, in line with the proposed strategy for ITT analyses for trials with incomplete outcome data as proposed by White et al.,⁷ sensitivity analyses were performed to explore the robustness of the main analyses in the mITT population and included analyses in all randomized patients (the ITT population). Please see “Sensitivity analysis” for details on page 12.

While conducting the study, it was observed that comorbidities had a negative impact on completeness of the follow-up data. To assess for a possible bias towards a selective data collection of healthier patients, treating physicians of patients that had dropped out of the study were contacted to obtain additional information on the general health status and level of functioning of these patients. Please see also “Patient replacement and missing data” on page 10.

Study methods

Outcomes - randomized controlled trial

Primary outcomes

The main clinical outcome was the change from baseline to 12 months after initiation of treatment in PDQ-39 (score 0-100).⁸

The primary health economic outcomes are elaborated on page 19.

Secondary outcomes

- PD motor symptoms -- Movement Disorder Society’s Unified Parkinson’s Disease Rating Scale (MDS-UPDRS) part III in on-drug state (score range 0-132) ²;
- Motor experiences of daily living-- MDS-UPDRS part II in on-drug phase (score range 0-52) ²;
- Dyskinesia -- Clinical Dyskinesia Rating Scale (CDRS, score range 0-28) in on-drug state ⁹;

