The primary objective of the economic evaluation is to estimate the cost-effectiveness and cost-utility of CLI treatment versus DBS treatment in the first year of follow-up after treatment initiation. The results of the cost-effectiveness analysis (CEA) allow for local decision making on the economically most optimal treatment approach for patients with PD, based on the clinically relevant health outcomes regarding quality of life in particular, while the cost-utility analysis (CUA) provides information for health policy decision makers to decide upon efficient and affordable health care in general, based on nationally accepted evaluation criteria regarding costs per QALY in view of patients' disease burden.

Types of economic evaluation

The economic evaluation of CLI against DBS was conducted alongside the INVEST clinical trial with individual patient-level data. The costs per unit change on the PDQ-39 summary index score at 12 months follow-up versus baseline and the costs per quality adjusted life year (QALY) were the primary economic outcomes. Incremental cost-effectiveness (ICER) and cost-utility (ICUR) ratios were calculated as the costs difference divided by the difference in effect for CLI minus DBS treatment.

Jurisdiction

The trial was conducted in the Netherlands, where health insurance is obligated for inhabitants and health care is offered by public and private providers.

Perspective, time horizon and discounting

Both health care and societal perspectives were taken into account with a time horizon of 12 months following index surgery. Because the time horizon was 12 months, no discounting was performed.

Cost components

Costs encompassed health care costs, out-of-pocket expenses by patients and family members and costs of productivity loss due to sick leave from work (absenteeism) or lowered efficiency while at work (presenteeism).

Sources

Health care costs covered the use of the following use of resources:

- screening for appropriateness of treatment indication;
- index treatments CLI with infusion devices or DBS with stimulation devices;
- emergency departments visits;
- inpatient hospital admissions at neurology, psychiatry, the intensive care, or other units;
- outpatient hospital consultations (*e.g.*, medical specialist, specialist nurse);
- diagnostic procedures (*e.g.*, imaging by MRI, CT, ultrasonography or X-ray);
- therapeutic procedures (*e.g.*, ex-plantation, revision tube or other material, medication);

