The primary health outcome in the cost-effectiveness analysis was the change in the PDQ-39 between baseline and 12 months after randomization. The change score showed the increase or decrease in number of difficulties across eight different dimensions of health (including mobility, activities of daily living, emotional well-being, and stigma) as experienced by patients in the preceding month. Dimension scores are coded on a scale of 0 (perfect health as assessed by the measure) to 100 (worst health as assessed by the measure). The change score was defined as the mean score on the eight scales at month 12 minus the mean score at baseline, in theory ranging from -100 to +100 with a score of 0 representing 'no change'.

The primary health outcome in the cost-utility analysis was the number of QALYs. Patient's health status was assessed with the EQ-5D-3L at baseline, one week, three months, six months, nine months, and 12 months post randomization. The EQ-5D contained five items: mobility, self-care, usual activities, pain/complaints, and mood (anxiety/depression).³¹ Each item had three response options: no problems, some problems, or serious problems. EQ-5D scoring profiles at successive measurements were converted into health utility scores using general population based tariffs of time trade-off ratings of health states.³² QALYs were calculated by taking the product sum of the health utility scores during follow-up and the interval lengths in years in-between successive measurements.

Health economic analysis methods

Analysis population

The CEA and CUA were done with the modified intention-to-treat population (see page 9) with references to the CONSORT-flow diagram in Figure SAP-1 and the baseline characteristics of the two RCT-subpopulations in Table EE1. Summary statistics for health utility scores at baseline were included in the manuscript text.

Cost-effectiveness threshold

The applied cost-effectiveness threshold for the sample size calculation was €120,000 as described and substantiated in the published study protocol.¹

Statistical decision rules

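### The HEAP gives conflicting time origins for its primary economic outcomes: surgery or treatment start for the evaluation, randomisation for PDQ-39 and EQ-5D

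*SAP*

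**What the plan says.** The HEAP uses two clocks.

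- **Treatment clock.** Under Perspective, time horizon and discounting, the evaluation is planned "with a time horizon of 12 months following index surgery". Under Objective, cost-effectiveness and cost-utility are to be estimated "in the first year of follow-up after treatment initiation".
- **Randomisation clock.** Under Health outcomes, the effect measure of the cost-effectiveness analysis is "the change in the PDQ-39 between baseline and 12 months after randomization". The utility measure is the "EQ-5D-3L at baseline, one week, three months, six months, nine months, and 12 months post randomization".

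The other parts of the plan count from treatment. The SAP (Primary outcomes) defines the main clinical outcome as "the change from baseline to 12 months after initiation of treatment in PDQ-39". Protocol 7.3 times every RCT visit after baseline from the start of the study treatment.

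These are different dates. In protocol 7.3, baseline assessment comes first, then multidisciplinary review of eligibility, then randomisation, then treatment: "Within 3 months after the baseline assessment the study-treatment" is to begin.

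The HEAP computes QALYs by multiplying utilities by the time between consecutive measurements and summing. It does not say how the stretch from baseline to treatment is handled.

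**The concern.** The cost-effectiveness and cost-utility ratios are the primary economic outcomes, and the section that defines their effect side contradicts the horizon of the same plan. If an analyst applies the Health outcomes text as written, the 12 QALY months start at randomisation, include untreated waiting time and stop before the treated year is complete.

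The wait may also differ by arm. Protocol 9.5 says most DBS centres have a waiting list, while CLI can be started at relatively short notice. A difference in waiting time could then appear as a difference in QALYs that has nothing to do with the treatments.

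Even if the references to randomisation are slips, the QALY rule is incomplete. The baseline EQ-5D may precede treatment by up to 3 months, and the next one comes 1 week after treatment start (protocol 7.3 and 12.4). Two analysts could both follow the rule and differ on whether the first interval is one week or about three months plus a week.

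**Working it through.** **1. The plan's own figure (protocol 4.4).** Inputs: cost difference €34,174 a year, willingness to pay €120,000 per QALY, SD 0.35 for QALYs and €10,000 for costs, zero correlation, 80% power, two-sided 5%.

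- Target: 34,174 / 120,000 = 0.2848 (the protocol prints 0.2847).
- SD of net health benefit: √(0.35² + (10,000/120,000)²) = 0.3598.
- Normal approximation: n = 2 × (1.96 + 0.84)² × 0.3598² / 0.2847² ≈ 25.1, so 26 per group. The exact t-test gives 26.07, with 79.9% power at 26.
- Dropout: 26 / 0.8 = 32.5, so 33 per group and 66 in total.

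The figure reproduces. No time origin enters it, so the point does not touch the sample size.

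**2. Size of the offset.** The 3-month limit runs from the baseline assessment, and randomisation comes later. The planned gap from randomisation to treatment is therefore 3 months less the time from baseline to randomisation. Three months is a ceiling.

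**3. Common lag, costs from surgery and QALYs from randomisation.** Assume the same lag of m months in both arms, no utility difference between arms before treatment and a constant one after it. The QALY window then holds (12 − m)/12 of the yearly difference, and the ratio is 34,174 / [0.2848 × (12 − m)/12].

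| Lag (assumed) | QALY difference seen | Cost per QALY | Factor |
|---|---|---|---|
| 0 months | 0.2848 | €120,000 | 1.00 |
| 1 month | 0.2611 | €130,909 | 1.09 |
| 2 months | 0.2373 | €144,000 | 1.20 |
| 3 months | 0.2136 | €160,000 | 1.33 |

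If costs were moved to the same shifted window and also accrued at a constant rate, the factor (12 − m)/12 would cancel and the ratio would stay at €120,000. The distortion comes from mixing clocks.

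**4. Wait differing by arm, QALYs over 12 months from randomisation.** Assume equal untreated utility and an equal gain g from either treatment, with one arm waiting d months longer. Spurious difference = g × d/12.

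- Smallest case: 0.1 × 1/12 = 0.008 QALY, which is 3% of 0.2847 and worth €1,000 at €120,000 per QALY.
- Largest case: 0.2 × 3/12 = 0.05 QALY, which is 18% of 0.2847 and worth €6,000.

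The gains and waits are assumptions; the documents give neither.

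**5. Intervals summed from the baseline date.** Here the QALY window lengthens with the wait. Each extra month adds u/12 to the arm that waits longer, for example 0.5/12 = 0.042 QALY at an assumed utility of 0.5. This runs opposite to step 4, where the longer-waiting arm loses QALYs. The text therefore leaves even the direction open. The HEAP's scenario analysis, which subtracts the whole baseline utility from the QALYs, is right only if the window is exactly one year.

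**6. PDQ-39.** This is a change between two time points. A different origin moves the final assessment and creates no accrual window.

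**The case against.** The best reply is that this is one repeated slip. The HEAP presents itself as an extension of the SAP, whose PDQ-39 outcome runs from treatment initiation. The months listed for the EQ-5D are those of the protocol schedule, which is timed from treatment start. No separate series timed from randomisation is planned. The cost questionnaires are completed at the same 3, 6, 9 and 12 month visits as the EQ-5D (protocol 7.3 and 12.4), so the data for both sides of the ratio come from the same visits. On waiting, protocol 9.5 goes on to say that study patients in both arms start within three months of baseline screening, expressly for comparability.

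Most of this stands. A reader might infer that costs run from surgery while effects run from randomisation, so that the two sides of each ratio are three months apart. The documents do not say so: the surgery horizon is stated for the whole evaluation, and no text gives costs their own origin. Costs even include pre-treatment screening.

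The reply does not settle the matter. The wrong origin is stated for both effect measures in the section that defines them. The QALY rule is silent on the wait under either reading. The common limit narrows a difference in wait between arms but does not exclude one.

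**Conclusion.** The point holds as an inconsistency that should be corrected: the HEAP states conflicting origins for its primary economic outcomes, and its QALY rule leaves the pre-treatment interval undefined. It does not show that mismatched windows will be used.

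Any bias arises only as far as the literal text is applied. Under the assumptions of steps 3 and 4, it is about 0.008 to 0.05 QALY for a 1 to 3 month difference in wait, or a cost-utility ratio inflated by 9 to 33% for a common lag of 1 to 3 months. The upper ends sit at a ceiling the planned gap does not quite reach. Actual waits are not reported.

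Two larger figures are tempting and should not be used:

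- Untreated time of 1 to 3 months at an assumed utility of 0.5 is worth 0.042 to 0.125 QALY. That is a level within each arm, and it cancels between arms if waits are equal.
- Two months of CLI equipment and infusion at the protocol's €45,000 a year is €7,500. This is no bias if costs run from surgery in both arms, because each arm then carries a full 12 months.

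**What to change.** In the HEAP:

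1. Under Health outcomes, replace both references to randomisation with start of study treatment.
2. Use that one origin for costs, QALYs and PDQ-39, and align the wording under Objective and under Perspective, time horizon and discounting. Say which dated event marks the start in each arm.
3. Carry the baseline EQ-5D forward as the utility at time zero. The QALY window is then exactly 12 months, the interval from baseline to treatment is not accrued, and the baseline-correction scenario is coherent.
4. State that screening costs are counted as a fixed pre-treatment item.
5. Report the time from baseline to treatment by arm.

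An analysis from randomisation can be offered as optional. It should be labelled as resting on interpolated utilities, because no EQ-5D or iMCQ is scheduled during the wait.

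The cost is a few lines of text and one descriptive table row. No new assessments are needed. Treatment-start dates must already be held, since the visits are timed from them, although the documents do not list them as a data item.
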